### **3.0. SAMPLE ELIGIBILITY CRITERIA**

**Child/Parent Inclusion Criteria and Rationale:** Children and parents/caregivers will be eligible if: 1) the child is 3 – 8 years of age at time of enrollment (intervention content is not age-appropriate for other children); 2) patients with an expected treatment course of at least 3 days to receive moderate to high intensity chemotherapy and/or radiation therapy either in-patient or outpatient (children receiving chemotherapy are at risk for high symptom distress; 3-day treatment course is required to deliver study conditions and contributes to sample homogeneity); and 3) one parent/caregiver ( $\geq 18$  years of age) can be present for all sessions (study targets both child and parent/caregiver).

**Child/Parent Exclusion Criteria and Rationale:** Children and parents/caregivers will be excluded if: 1) the child and/or parent/caregiver do not speak English or 2) the child has a significant cognitive impairment that might hinder participation (determination made in consultation with attending physician, oncologist, and parents).

**Sample Size.** We will recruit a total sample size of 184 child and parent/caregiver dyads (368 total) and assume 15% attrition in order to retain 156 child and parent/caregiver dyads (78 dyads/group) at Time 3.

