**Data Collection & Randomization Procedures.** Following consent, the project manager will arrange a time for parents/caregivers to complete baseline (T1) measures during a routine clinic visit, prior to their next scheduled chemotherapy admission. A trained evaluator will administer measures in a quiet/private setting and remain available for questions. The child/parent or caregiver dyad will then be stratified by child age (preschoolers 3-5 years; school-agers 6-8 years) and randomized in blocks of six to the AME or attention control condition by our statistician. After the PI or project manager from the enrolling site receives randomization status from our study statistician, she will inform the parent/child of their randomization status and will then immediately schedule Session 1. Only the

project manager, PI, statistician, and intervener will know the child/parent dyad's randomization status. Evaluators will be blinded.

[figure not shown]
All study condition sessions will be video recorded to facilitate collection of child engagement and parent-child interaction data and monitor treatment fidelity. Sessions 1 and 2 are video recorded to desensitize children/parents to video recording; only Session 3 video data are analyzed for Aim 1. In our previous studies, video recording did not negatively affect participant accrual. An evaluator, blind to randomization status, will administer T2 measures after Session 3. Evaluators will administer T3 measures 30 days (+/- 7 days) post-intervention during a subsequent clinic visit or by telephone. Parent self-reports will be used to monitor use of study condition activities between sessions and between T2 and T3 data collections (Appendix 1).

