**Main analyses:** For analyses below we will analyze as randomized and attempt to collect outcome data on non-completers, following the intent-to-treat principle. For Aims 1 and 2, each outcome will be modeled separately. Also we will model T2 separately from T3. Thus, there will be a total of 12 models in Aim 1 (6 outcomes x two time points). In Aim 2, two outcomes will be examined and 3 potential moderators at two time points for a total of 12 (2 outcomes x 3 moderators x 2 time points) models. For Aim 1, our primary goal is to test mediation effects. Mediation effects will be estimated in an ANCOVA setting, fitting the appropriate mediation models using MPlus and then testing indirect effects using the percentile bootstrap approach to estimate the indirect effect. The multiple mediation model with three-path mediation effects specifies that the intervention will act through the proximal and distal mediator on the outcome and also have a direct effect on the outcome. Each outcome model will have 6 key predictors (intervention, two proximal mediators, 3 distal mediators), and control for T1, age (3-5 years vs. 6-8 years), site, and any imbalanced baseline covariates found above (allowing for up to 6 imbalances). Thus we will have up to 15 variables in any model. For Aim 2, we will test moderation effects by including the appropriate interaction terms of the potential moderator (dichotomized at the median) with the intervention indicator (AME vs. attention control) in our models. For all models in Aims 1 and 2, we will assess goodness-of-fit (GOF) using standard GOF measures (comparative fit index, root mean square error of approximation, and root mean square residual). For Aim 3, an exploratory aim, we will use ANCOVA to compare changes in child symptom distress at T2 and T3 between intervention and control groups. In light of positive findings, we next will explore models as in Aims 1 and 2 to assess for potential mediation and moderation effects for this outcome.

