**Missing data and multiple comparisons:** We will compare all baseline variables between subjects who drop out of the study and those who do not using two-sample *t* tests, chi-square tests, or their non-parametric equivalents as appropriate. MPLUS software will incorporate participants who drop out before completion by using the MPLUS imputation method to perform a bias adjustment for missing data under maximum likelihood estimation and the assumption that data are missing at random. If we find that missing data are not missing at random, we will use a pattern mixture modeling approach to address; however, based on our prior studies we expect limited attrition (<15%) and little to no missing data on instruments (<1%). As our primary outcomes are child (CHQ) and parent emotional/traumatic (POMS) distress and other outcomes are considered secondary, we do not plan on adjusting *p* value for multiple comparisons for the primary outcomes but will apply the Hochberg step-up procedure for the secondary outcomes.

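### The T3 models and their missing-data method do not use the T2 score of the same outcome; bias in the T3 treatment effect is possible, not given, and naming T2 as an auxiliary variable prevents it at almost no cost

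*Combined protocol and SAP*

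**What the plan says.** Section 7.0 (Main analyses) separates the two follow-up times: "Also we will model T2 separately from T3". It counts the Aim 1 models accordingly: "there will be a total of 12 models in Aim 1 (6 outcomes x two time points"). It then gives their contents: "Each outcome model will have 6 key predictors (intervention, two proximal mediators, 3 distal mediators), and control for T1, age", followed by site and up to six baseline covariates found to be imbalanced. The T2 value of the outcome is not on the list for the T3 model.

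Section 7.0 (Missing data and multiple comparisons) keeps dropouts in the analysis through Mplus, "under maximum likelihood estimation and the assumption that data are missing at random". No auxiliary variable is named. The check on dropout compares baseline variables only. Pattern-mixture modelling is the fallback if data prove not to be missing at random.

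On numbers, Section 3.0 says "We will recruit a total sample size of 184 child and parent/caregiver dyads" and "assume 15% attrition in order to retain 156 child and parent/caregiver dyads (78 dyads/group) at Time 3".

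The table in Section 6.0 schedules most outcomes at T1, T2 and T3, but the CHQ Mental Health Subscale at T2 and T3 only. Section 7.0 names the CHQ as a primary outcome and also says that all models adjust for the baseline value of the outcome.

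**The concern.** Maximum likelihood under missing at random conditions only on the variables given to it. Where only the T3 outcome is missing, a dyad without T3 still informs the mediator equations but adds nothing to the equation for the T3 outcome. The assumption then reads: given arm, mediators, T1, age, site and covariates, dropout is unrelated to T3 distress. T2 is measured after Session 3 and T3 about 30 days later, so dyads lost in between have a recent score on the same scale that goes unused.

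If distress at T2 affects who returns, beyond what the listed variables explain, that assumption fails although the variable needed to restore it is in the database. The planned dropout check would not show this, because it stops at baseline, and the pattern-mixture fallback is used only after a problem has been found. The matter weighs most for the CHQ: if the Section 6.0 schedule is right, its T2 score is its only measurement before T3.

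**Working it through.** **1. The plan's own figure.** 156 / (1 - 0.15) = 183.5, rounded up to 184; check 184 x 0.85 = 156.4. The figure reproduces, and 184 - 156 = 28 dyads are expected without T3. The documents do not say how many of the 28 leave after T2.

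**2. Assumptions, none of them in the documents.** T1-T2 and T1-T3 correlation 0.5; T2-T3 correlation 0.7; 15% loss in each arm; log-odds of dropout 0.5 to 1.0 per SD of T2; for precision, a T2-T3 correlation given the other model variables (rho) of 0.3 to 0.8.

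**3. Precision.** Variance with T2 divided by variance without T2 = 1 - rho^2 x d, where d is the share of dyads with T2 who lack T3.

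- All losses after T2, d = 0.15. For rho = 0.3: 1 - 0.09 x 0.15 = 0.9865, so the SE falls 0.7%. For rho = 0.8: 1 - 0.64 x 0.15 = 0.904, so the SE falls 4.9%.
- Half of the losses after T2, d = 0.075 / 0.925 = 0.081. The SE falls 0.4% to 2.6%.
- With all losses after T2, effective N at T3 rises from about 156 to between 158 and 173. At an assumed effect of 0.449 SD (80% power with 78 per arm, two-sided 0.05), power rises from 0.80 to between 0.806 and 0.839.

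**4. Bias by hand, dependence in one arm only.** In that arm, dropout probability p is logistic in T2 with slope beta and mean 0.15. The mean of T2 among retained dyads shifts by beta x V x E[p(1-p)] / 0.85, where V is the T2 variance not explained by T1. Since E[p(1-p)] is at most 0.15 x 0.85, the shift is at most 0.15 x beta x V. Multiplying by the slope s of T3 on T2 gives a ceiling on the bias in the T3 treatment effect.

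- With T1: V = 1 - 0.5^2 = 0.75 and s = (0.7 - 0.5 x 0.5) / 0.75 = 0.60. For beta = 0.5: 0.15 x 0.5 x 0.75 x 0.60 = 0.034 SD. For beta = 1.0: 0.068 SD.
- Without T1: V = 1 and s = 0.7. For beta = 0.5: 0.053 SD. For beta = 1.0: 0.105 SD.

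**5. Bias by simulation.** 184 dyads, 15% loss, 4,000 runs per scenario, dependence in one arm only, T2-T3 correlation 0.7:

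| Variables in the T3 model | beta 0.5 | beta 1.0 |
|---|---|---|
| Arm and T1 | 0.033 | 0.058 |
| Arm, T1 and one T2 mediator (correlation 0.5 with T2) | 0.024 | 0.045 |
| Arm only (CHQ as scheduled) | 0.041 | 0.099 |

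Monte Carlo error is about 0.002 to 0.003. In the last row the estimates that include T2 were themselves off by -0.009 and 0.006 in the same runs, so the part due to leaving T2 out is 0.041 + 0.009 = 0.050 and 0.099 - 0.006 = 0.093. A separate simulation without T1, with one mediator and a true effect of -0.40, gave estimates of -0.36 to -0.32, a bias of 0.04 to 0.08. Together these support about 0.03 to 0.06 SD with T1 and 0.04 to 0.09 SD without it.

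With T2 as an auxiliary variable, bias is at most 0.01 SD in every scenario. The SE of the effect is 0.13 to 0.16 SD, so 0.058 is about 0.4 of a standard error (0.058 / 0.139).

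**6. Other dropout patterns.** If dropout is unrelated to T2, bias is zero. If it depends on T2 equally in both arms, bias is about 0.02 SD or less. If it depends on T2 in opposite directions, bias reaches 0.12 SD with T1 and 0.18 SD without; nothing in the documents points to that pattern.

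**7. Indirect effects.** With T2 mediators fully observed, one-arm or equal dependence moves the indirect effect by 0.001 to 0.006 SD on about 0.10 with one mediator, and by at most 0.010 SD on about 0.20 with three. One other set-up gave at most about 0.02 SD. The bias sits almost wholly in the direct path.

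**The case against.** Three objections carry weight.

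- The exclusion of T2 is read from silence. Section 7.0 lists predictors of the analysis model and refers to an Mplus imputation method without listing its variables, so the sponsor may intend to include T2. This stands as far as intent goes. The text still does not say so, and choosing auxiliary variables after seeing the data is avoidable discretion.
- The primary goal of Aim 1 is the bootstrapped indirect effect, which barely moves. This stands: the point concerns the direct path in Aim 1 and the T3 group comparison in Aim 3. Treatment effects at T3 in Aim 2 may be affected too, but interactions were not simulated.
- The plan already limits the damage. It seeks outcome data from non-completers, allows T3 by telephone within a window of 7 days either side, and expects attrition below 15%. T2 distal mediators, if they enter the T3 model, recover part of the information. This reduces the size but does not remove the point.

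A reader might also infer more than the documents support. Fitting T2 and T3 separately is not an error, and nothing here requires a joint model. Nor can one say that the T3 results will be biased or that the missing-at-random assumption is violated. That needs dropout tied to T2 beyond the listed variables and, for anything above about 0.02 SD in the treatment effect, tied differently by arm. The documents give no evidence of this: both arms have the same session length, contact schedule and a kit to keep.

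**Conclusion.** The gap is real and small. As the plan is written, the T2 outcome scores of dyads lost before T3 play no part in the T3 models. The consequence is conditional: about 0.03 to 0.06 SD in the T3 direct or total effect with a T1 value, and about 0.04 to 0.09 SD for the CHQ as scheduled, if dropout depends on T2 in one arm only. Otherwise it is about 0.02 SD or less under equal dependence, about 0.01 SD for indirect effects, and 0.4% to 5% in standard error. If dropout rises with distress among controls, retained controls look better than they should and a true benefit is understated.

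These sizes rest on assumed correlations, dropout slopes and timing of losses. They also assume that mediators are measured by T2. The plan does not say which time point of family normalcy and parent self-efficacy enters the T3 model; if the T3 values do, they would be missing together with the outcome, and the indirect-effect figures would not apply. The change is worth making because it is cheap and covers a primary outcome, not because the main mediation result is at risk.

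**What to change.** Add to the missing-data paragraph of Section 7.0: *In every T3 model, the T2 value of the same outcome enters as an auxiliary (missing-data) variable, not as a predictor.* Extend the dropout comparison: *T2 scores of dyads lost between T2 and T3 will be compared with those of dyads retained at T3.*

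The T2 score must not become a covariate in the T3 outcome equation, since that would remove the part of the treatment effect already present at T2 and change what is estimated.

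The cost is two sentences and slightly more model set-up, including carrying the auxiliary variable through each bootstrap resample. No new data are collected. The separate T2 and T3 models, the sample size of 184 and the estimands stay as they are.

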## **2.0. OBJECTIVES AND SPECIFIC AIMS**

The objectives of this two group randomized controlled trial is to identify behavioral, sociological, and psychological variables contributing to positive outcomes observed in previous AME studies (i.e., mediators) and identify for whom the intervention works (i.e., moderators). We will examine proximal mediators of child engagement and parent-child interaction and distal mediators of perceived family normalcy, parent confidence (self-efficacy) about their ability to support their child during treatment, and independent parent/child use of music play to manage distress during hospitalization. We hypothesize that these factors mediate change in outcomes of child emotional distress, physical symptom distress, and quality of life; parent emotional/traumatic distress and quality of life; and family function. Published literature and our parent interview data support the proposed mechanisms of action; therefore, a mechanistic study of mediators and moderators of intervention effects is the next logical step. In some instances we will consent the child's caregiver if they are currently fulfilling the role of the parent. Specific aims and hypotheses are to:

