### **Aim 1: Examine the effects of proximal and distal mediators of the Active Music Engagement (AME) intervention on outcomes for young children with cancer and parents.**

Hypothesis 1.1: Child engagement and parent-child interaction (proximal mediators) will mediate the effect of AME on perceived family normalcy, parent self-efficacy, and independent parent/child use of music play.

Hypothesis 1.2: Perceived family normalcy, parent self-efficacy, and independent parent/child use of music play (distal mediators) will mediate the effect of AME on child outcomes (emotional distress, quality of life), parent outcomes (emotional distress, traumatic distress, quality of life), and family function immediately post-intervention (Time 2) and 30 days post-intervention (Time 3).

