### **Aim 2: Examine moderators of the AME intervention on outcomes for young child and parent distress.**

Hypothesis 2.1: Child and parent distress with prior hospitalizations and child age will moderate intervention effects for child emotional distress and parent emotional/traumatic distress outcomes at Time 2 and Time 3.

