## 5.0. RESEARCH DESIGN, METHODS, AND PROCEDURES

**Conceptual Framework.** Our conceptual framework (Figure 1) is based on [name]'s Contextual Support Model of Music Therapy and further informed by Kazak's Pediatric Medical Traumatic Stress Model, which provides a useful heuristic for understanding short and long-term consequences of pediatric cancer treatment for parents and their child. In our conceptual framework, recurring events related to cancer treatment (i.e., hospitalizations, procedures) are viewed as potentially traumatic events. Parent appraisal of events as traumatic or not traumatic is influenced by pre-existing factors, which serve as antecedents in our study.

Published research indicates that higher parent and child distress during cancer treatment and survivorship is related to: 1) demographics (younger child/parent age, female parent gender, and lower socio-economic status/education), 2) higher parent/child distress with prior hospitalizations, and greater traumatic stress symptoms, and 3) disease and treatment characteristics (diagnosis, relapsed disease, greater treatment intensity).

Figure 1: Conceptual Framework

The AME directly targets the proximal mediators of child engagement and parent-child interaction, as well as distal mediators of perceived family normalcy, parent confidence (self-efficacy) about their ability to support their child during treatment, and independent music play between therapist-led sessions.

[figure not shown]
Our study examines proximal and distal mediators of the AME on outcomes for young children (emotional distress, physical symptom distress (exploratory), quality of life), parents (emotional distress, traumatic distress, quality of life), and family function. In addition, we examine moderators of the AME intervention on outcomes (child/parent distress with prior hospitalizations; child age). This study will allow us to determine *how* and *for whom* the intervention works, informing a subsequent trial to examine cumulative impact/efficacy of AME across repeated cancer treatment admissions to manage distress and prevent traumatic stress symptoms in survivorship. Findings will also have implications for use of the CSM-MT to guide development of active music interventions to manage treatment distress in other populations.

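### Aim 2 counts two outcomes where Hypothesis 2.1, counted as in Aim 1, has three; read with the primary outcome definition, parent traumatic distress (IES-R) gets no moderation test

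*Combined protocol and SAP*

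**What the plan says.** Section 7.0 (Main analyses) sets one modelling rule for both aims: "For Aims 1 and 2, each outcome will be modeled separately". T2 and T3 are also modelled separately. It then gives a count for each aim. For Aim 1 it is "12 models in Aim 1 (6 outcomes x two time points"). For Aim 2: "In Aim 2, two outcomes will be examined and 3 potential moderators at two time points for a total of 12" models. The two Aim 2 outcomes are not named.

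The hypotheses in Section 2.0 define what is to be counted. Hypothesis 1.2 lists two child outcomes, then "parent outcomes (emotional distress, traumatic distress, quality of life"), then family function. Hypothesis 2.1 claims moderation for "child emotional distress and parent emotional/traumatic distress outcomes at Time 2 and Time 3".

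The measures table in Section 6.0 gives two parent distress instruments, the POMS short form (37 items) and the IES-R (22 items), each collected at T1, T2 and T3. They share one row label, but no combined score is described.

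The paragraph on missing data and multiple comparisons in Section 7.0 attaches instruments to the primary outcomes: "As our primary outcomes are child (CHQ) and parent emotional/traumatic (POMS) distress and other outcomes are considered secondary". Primary outcomes are not adjusted for multiplicity; secondary outcomes go through the Hochberg procedure.

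**The concern.** The same pair of constructs is counted as two outcomes in Aim 1 and apparently as one in Aim 2, although one modelling rule governs both. The only place that attaches an instrument to the slashed term names the POMS, which measures mood, and leaves out the IES-R, the outcome scale for traumatic stress.

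Three things are at stake. First, part of Hypothesis 2.1 may have no prespecified test. Traumatic stress is central to this trial: the rationale in Section 1.0 and the conceptual framework in Section 5.0 both build on it. Second, because the plan never names the Aim 2 outcomes, a moderation result reported for parent emotional/traumatic distress could rest on either scale, and the choice could be made after results are seen. Third, the choice decides multiplicity: the POMS is primary and unadjusted, while the IES-R falls among the secondary outcomes under Hochberg.

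**Working it through.** This is a direct count; no sample size or power input enters.

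**Inputs**
- Aim 1 outcomes (Hypothesis 1.2): child emotional distress, child quality of life, parent emotional distress, parent traumatic distress, parent quality of life, family function.
- Aim 2 outcomes (Hypothesis 2.1): child emotional distress and parent emotional/traumatic distress.
- Aim 2 moderators (Hypothesis 2.1): three, namely earlier hospital-related distress in the child, the same in the parent, and the child's age.
- Time points: two (T2, T3).

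**Formulas**
- Aim 1 models = outcomes x time points.
- Aim 2 models = outcomes x moderators x time points.

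**The plan's own figures**
- Aim 1: 6 x 2 = 12, as stated.
- Aim 2: 2 x 3 x 2 = 12, as stated.

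The multiplication is right in both cases. The question is what was counted.

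**One convention applied to both aims**

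| Parent emotional and traumatic distress | Aim 1 outcomes | Aim 1 models | Aim 2 outcomes | Aim 2 models |
|---|---|---|---|---|
| Two outcomes | 2 + 3 + 1 = 6 | 6 x 2 = 12 | 1 + 2 = 3 | 3 x 3 x 2 = 18 |
| One outcome | 2 + 2 + 1 = 5 | 5 x 2 = 10 | 1 + 1 = 2 | 2 x 3 x 2 = 12 |
| Stated in Section 7.0 | 6 | 12 | 2 | 12 |

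Neither convention gives the stated pair of 12 and 12.

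**Does the slashed term mean one outcome or two?** The objectives paragraph in Section 2.0 writes "parent emotional/traumatic distress and quality of life; and family function". Section 5.0 spells out the same set as "parents (emotional distress, traumatic distress, quality of life), and family function". So the document itself uses the slash for a pair that it elsewhere lists as two.

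**Could Aim 1 reach six with the pair merged?** The objectives paragraph also has six entries when the pair is merged: child 3 (including physical symptom distress) + parent 2 + family 1 = 6. That does not rescue the count. Hypothesis 1.2 omits physical symptom distress, and both Section 2.0 and Section 7.0 place it in the exploratory Aim 3.

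**What drops out**
- If the two Aim 2 outcomes are the CHQ and the POMS, the absent models are 18 - 12 = 6. These are 1 instrument (IES-R) x 3 moderators x 2 times = 6, and 6/18 = 33%.
- If the parent outcome were instead the IES-R, the same six models would be absent for the POMS, a named primary outcome.

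**The case against.** The best defence is that the 12 is deliberate. Section 7.0 names exactly two primary outcomes, the CHQ and the POMS, and Hypothesis 2.1 uses almost the same pair of labels. Limiting moderation to primary outcomes is a sensible choice, and nothing obliges Aim 2 to cover every Aim 1 outcome: it already leaves out quality of life and family function. On this view no model is missing and the only fault is a label wider than the instrument. The IES-R is also secondary and is still modelled in Aim 1.

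Much of this stands. The primary outcome pair is the likely source of the figure two, and the shortfall of six models exists only if Hypothesis 2.1 was meant to cover the IES-R. But the plan never says that Aim 2 is limited to primary outcomes, and Hypothesis 2.1 still promises a result on traumatic distress. Under the defence, that result would come from a mood scale. The mismatch between hypothesis and analysis remains.

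A second defence is a combined POMS and IES-R score. The measures section refers to Appendix 1, which is not in the text available here, so its absence cannot be fully confirmed. However, a composite would conflict with the Aim 1 count of six and with the primary outcome definition, which attaches only the POMS.

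**Conclusion.** The concern holds. Counting the parent outcomes as Aim 1 does gives 18 Aim 2 models against the 12 stated, and no single counting rule gives both stated totals. That the documents are inconsistent is certain. That the IES-R is the omitted instrument is an inference from the primary outcome definition, because the plan does not name the Aim 2 outcomes. On that reading, six of 18 moderation models (one third) have no place in the plan, and part of Hypothesis 2.1 goes untested.

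The effect is confined to Aim 2. The Aim 1 count and the choice of primary outcomes are unaffected. It should be corrected before analysis, but it does not threaten the trial's main results.

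**What to change.** The sponsor should first state its intent, then make one of two edits.

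1. **If moderation of traumatic distress is to be tested:** in the Main analyses paragraph of Section 7.0, name the Aim 2 outcomes as CHQ, POMS and IES-R and change the count to 3 x 3 x 2 = 18. In the multiple comparisons paragraph, call the POMS outcome parent emotional distress and confirm that the IES-R is secondary under Hochberg, as the present text already implies. State which tests form the Hochberg family.
2. **If it is not:** remove traumatic distress from Hypothesis 2.1, name the two outcomes as CHQ and POMS, correct the POMS label in the multiple comparisons paragraph in the same way, and keep 12 models.

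The second route costs only wording. The first adds six models on data already scheduled for collection, with no new visits or participants. Its drawback is a stricter threshold for the IES-R interaction tests. If the Hochberg family were those six tests and two-sided alpha were 0.05 (the documents state neither), a single isolated signal would need p <= 0.05/6 = 0.0083.
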